3. *Country and site within country.* We denote the country by X_i^2 , which will be 0 for US locations and 1 for Indian locations; X_n^4 is 1 only for patients in the second Indian site and 0 otherwise, while X_{iz}^4 is 1 only for patients in the second US site and 0 otherwise. As mentioned under the Primary analysis, we propose to fit models with country only, drug by country interaction, and with a drug by country interaction, including site within country as well. Analysis will be conducted within each site, then pooling the sites within country together. Further details regarding pooling across centers are provided above under the main prespecified analysis.

4. *Best spectacle-corrected visual acuity (BSCVA).* The primary outcome variable for this secondary outcome will be the change in best spectacle-corrected visual acuity from baseline to final (as defined in the FAST MOP, i.e. for those who successfully control inflammation as defined in the MOP, or at the time of failure for those who fail; MOP, Section 2.6). Visual acuity change scores are available for both eyes for each patient.

The primary analysis will use a linear mixed-effects regression, where the outcome variable is the change in BSCVA in each eye, using treatment assignment as a statistical predictor (regressor, independent variable); a random effect will be used at the individual level, because of the possibility that changes in the two eyes from a given patient are correlated. In a supplementary analysis, we will include as predictors (independent variables) anatomic location of uveitis, interaction between anatomic location and treatment assignment, and the study site, together with a random effects for patient. We will fit these models using maximum likelihood (R procedure `lmer`) and use likelihood-ratio tests to test the hypothesis that treatment assignment affects BSCVA change. Only eyes that are eligible and meet inflammation criteria at baseline will be included in this analysis. If at a given visit, vision cannot be assessed, we will carry the last observation forward. Additional sensitivity analyses for missing data will be used (including mixed effects models controlling for time, including all data from an individual).

Also, if there is no eye at Month 6 to assess, the patient will be given a logMAR value of 2.0.

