Because of the possibility that the outcome variable (BSCVA change score) will exhibit non-normality, we will repeat the analyses using transformations of the outcome data (including power and log transformations, or more general monotone transformations).

Additional analyses will be performed using age, gender, ethnicity, and the steroid dose at each month as predictors.

An additional supplemental analysis will be conducted using final BSCVA (instead of the change score) as the outcome, and including baseline BSCVA in each eye as a predictor, using methods otherwise identical to those above.

5. *Quality of life.* We will also use a linear mixed model to assess health-related quality of life, measured by the SF-36 questionnaire (PCS and MCS scores) and vision related quality of life NEI-VFQ-25 and IND-VFQ at 6 months or at the time of failure, as described in the Manual

of Operations. Predictors will be baseline quality of life, age, gender, ethnicity, study site (as a random effect), and treatment assignment, and we will test the hypothesis that the regression coefficient corresponding to treatment assignment equals zero using the Wald t-test. Similar assessments will be performed for vision-related quality of life questionnaires.

6. *Reason for discontinuation.* Individuals who discontinue study medication may do so due to inability to tolerate side effects, due to lack of efficacy, or for safety reasons. The outcome variable is whether the person discontinued due to intolerance, discontinued due to lack of efficacy, discontinued due to safety, or did not discontinue the medication. Because study site may be an important factor, we will use polytomous regression to model the discontinuation result as a function of treatment assignment (using a fixed effect for study site).⁷ If evidence is found that treatment assignment influences discontinuation result, further analyses may be conducted to determine whether or not treatment assignment is associated with discontinuation due to intolerance, lack of efficacy, or to safety, or some combination of these. We propose to classify all individuals in a two by four table according to treatment assignment and discontinuation (not discontinued, discontinued due to intolerance, discontinued due to lack of efficacy, discontinued due to safety) and conduct the Fisher's exact test (in its $r \times c$ form). The use of an overall test prior to further analysis is designed to protect the overall error rate.

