3.4 Sample Size Evaluation

3.4.1 Primary Calculation

The sample size for the trial will be 216 subjects, which we anticipate will provide approximately 80% power to detect a difference of 20% in the proportion of patients achieving control of inflammation at six months between the methotrexate and mycophenolate mofetil groups.

This sample size was determined based on the primary objective (superiority comparison of mycophenolate mofetil to methotrexate) and primary endpoint (treatment success). We assumed an effect size of 20%, as this was deemed to be clinically meaningful, and well within the distribution of the investigators' prior beliefs from published retrospective studies.

An approximate sample size is provided by the formula

$$2N = \frac{4(Z_{\alpha} + Z_{\beta})^2 \bar{p}(1-\bar{p})}{(p_c - p_i)^2} \quad (5)$$

(see Friedman et al. 2010), where α is the significance level (0.05, two sided), β is one minus the power (the desired power is 80%), p_c is in this case the probability of success in the methotrexate group (we estimate this at 0.4), p_i is the probability of success in the mycophenolate mofetil group (we estimate this at 0.6), and \bar{p} is $\frac{1}{2}(p_i+p_c)$. We assume 10% will be lost to follow-up in the first six months; details are given in the full proposal. This yields approximately 108 patients in each of the two groups, for a total of $2 \times 108 = 216$ subjects.

A power table is provided below as a sensitivity analysis (to show how the detectable effect size changes with varying success rates).

Success rate with Drug A	80% Power		90% Power	
	Detectable effect size	Success rate with Drug B	Detectable effect size	Success rate with Drug B
20%	18%	38%	21%	41%
30%	20%	50%	23%	53%
40%	20%	60%	23%	63%
50%	20%	70%	22%	72%
60%	19%	79%	21%	81%

Simulation confirms that this method yields adequate sample sizes for the logistic regression (results not shown).

Note that for the final analysis, the critical value will be adjusted slightly because of the interim analysis.

Sample size readjustment

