3.4.2 Power for Subgroup Analyses and Other Analyses

Subgroups in Specific Aim 1.

The prespecified subgroup analysis for specific aim 1 is to examine the difference between the methotrexate and mycophenolate mofetil groups within each anatomic location. Using Equation (5), we anticipate having in excess of 80% power to detect a difference of 25% in success rates.

The power for selected secondary outcomes is provided here.

Secondary Outcomes in Specific Aim 1.

1. *Twelve-month endpoint for success.* We assume an additional loss of 5% between 6 and 12 months (that is, in addition to the 10% already lost to follow-up in the first six months). **We expect approximately 78% power to detect a 20% difference in success rates at the 12-month endpoint.**

2. *Time to corticosteroid sparing control of inflammation.* For sample size planning, we use the approximate formula given in Friedman et al (2010) for the number in each group:

$$N = \frac{(Z_\alpha + Z_\beta)^2 (\phi(\lambda_C) + \phi(\lambda_I))}{(\lambda_I - \lambda_C)^2}$$

where λ_C is the hazard in the methotrexate group, λ_I is the hazard in the mycophenolate mofetil group, and $\phi(u) = \frac{u^2}{1 - e^{-uT}}$

where T is the censoring time (6 months). Previous studies suggest a median success time of approximately 3.5 months for mycophenolate mofetil.¹² **Assuming a 10% loss to follow-up, 108 subjects in each group provides 80% power to detect a difference of 2.47 months in the expected difference.** (Note: λ_C is $\log(2)/3.5$ mo. for this calculation.) We assume an alpha of 0.05 (two sided).

3. *Change in BSCVA.* For sample size planning, we assume a T-test comparing change scores between the two drugs, assuming a standard deviation of the change in visual acuity of 6.5 letters.^{13, 14} The sample size of 108 will provide approximately 80% power to detect 2.63 letters of difference in the change score. In other words, **we expect to have 80% power to detect whether mycophenolate mofetil yields 2.63 letters more of improvement than methotrexate, and we will have greater power to detect greater differences.** The power formula is provided in Chow et al and is computationally implemented in R in the function `power.t.test` (which we used).¹⁵

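### The principal visual acuity test uses the change score without baseline acuity, while the baseline-adjusted model, at least as precise in large samples, is only supplemental

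*Combined protocol and SAP*

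**What the plan says.** SAP 3.2.2, Planned Secondary Analyses, item 4 defines the endpoint: "The primary outcome variable for this secondary outcome will be the change in best spectacle-corrected visual acuity from baseline to final". The main analysis is a linear mixed model with a patient random effect, "where the outcome variable is the change in BSCVA in each eye, using treatment assignment as a statistical predictor", tested by likelihood ratio. Only eyes meeting the inflammation criteria at baseline enter, so a patient contributes one or two eyes.

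The first supplementary model adds "anatomic location of uveitis, interaction between anatomic location and treatment assignment, and the study site", but not baseline acuity. Baseline acuity appears only in a later paragraph of item 4: "An additional supplemental analysis will be conducted using final BSCVA (instead of the change score) as the outcome, and including baseline BSCVA" for each eye as a predictor, with methods otherwise the same.

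Two neighbouring items do it the other way round. Item 5 (quality of life) has the baseline score among the predictors of its main model. Item 9 (macular thickness) tests treatment in a model that contains baseline thickness.

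For power, SAP 3.4.2 item 3 uses a t-test on change scores, "assuming a standard deviation of the change in visual acuity of 6.5 letters", and concludes: "The sample size of 108 will provide approximately 80% power to detect 2.63 letters of difference in the change score".

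**The concern.** Baseline acuity is measured on every eye and is likely to be a strong predictor of final acuity. Leaving it out of the principal model discards information already in hand. The estimate also responds to whatever baseline difference chance produces between the arms. Randomization is blocked within site only (SAP 2.4.1 and 2.4.3), so nothing in the design balances baseline acuity.

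The SAP accepts this reasoning elsewhere. SAP 3.4.2 item 4 credits the baseline score with reducing the SF-36 SD from 8.4 to 6.72, and item 7 says that adjusting for baseline thickness would raise power. No reason is given for treating acuity differently.

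The label matters because SAP 3.2.2 undertakes to keep the single prespecified test apart from supplemental ones when reporting. If the two acuity models disagree, the plan makes the change score the finding, and a switch at that stage would look data-driven.

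**Working it through.** **Inputs.** Change SD 6.5 letters and 108 per arm (SAP 3.4.2 item 3). Loss to follow-up: "We assume 10% will be lost to follow-up in the first six months" (SAP 3.4.1), so 108 × 0.9 = 97.2, taken as 97 per arm. Two-sided tests (SAP 3.2.2). An alpha of 0.05 is assumed, since item 4 states none. The documents give no baseline-to-final correlation ρ for acuity; the 0.6 in SAP 3.4.2 item 4 is for the SF-36. A range is therefore shown.

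**The plan's own figure.** A two-sample t-test with SD 6.5 and 97 per arm has 80% power at 2.628 letters, and power at 2.63 letters is 80.1%. With 108 per arm and no loss the detectable difference would be 2.49 letters. The stated 2.63 is therefore right and already allows for the 10% loss.

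**Variance under each model.** Let s_B and s_F be the SDs of baseline and final acuity.

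- Change score: s_B² + s_F² − 2ρ·s_B·s_F
- Baseline-adjusted residual: s_F²(1 − ρ²)
- Difference: (s_B − ρ·s_F)², which is never negative and is zero only when the slope of final on baseline, ρ·s_F/s_B, equals 1

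With equal variances s², the two are 2s²(1 − ρ) and s²(1 − ρ²). Their ratio is (1 + ρ)/2, so the adjusted SD is 6.5 × √((1 + ρ)/2). The detectable difference scales with the SD: (2.628/6.5) × SD = 0.4043 × SD.

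| ρ | Adjusted SD | Detectable at 80% power (letters) | Power at 2.63 letters |
|---|---|---|---|
| change score | 6.50 | 2.63 | 80% |
| 0.6 | 5.81 | 2.35 | 88% |
| 0.8 | 6.17 | 2.49 | 84% |
| 0.9 | 6.34 | 2.56 | 82% |
| 0.95 | 6.42 | 2.59 | 81% |

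**Which ρ fits a change SD of 6.5?** With equal variances, 6.5 = s√(2(1 − ρ)), so s = 6.5/√(2(1 − ρ)). This gives an acuity SD of 7.3 letters at ρ = 0.6, 10.3 at 0.8, 14.5 at 0.9 and 20.6 at 0.95. On acuity itself, Protocol 2.3.3 excludes only hand motion or worse in the better eye, and the score runs up to 100 letters (Protocol 5.2.2.B). An SD of 7 to 10 letters looks narrow for such a population. If the SD is 15 to 20 letters (an assumption; the documents give none), ρ = 1 − 6.5²/(2s²) is 0.91 to 0.95.

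**Sensitivity to chance imbalance.** With equal variances, a baseline difference d moves the change-score contrast by (1 − ρ)d in size. For an imbalance of 1.96 standard errors, d = 1.96·s·√(2/97). Substituting for s, the shift is 1.96 × 6.5 × √(2/97) × √((1 − ρ)/2) = 1.83 × √((1 − ρ)/2). That is 0.82, 0.58, 0.41 and 0.29 letters at ρ = 0.6, 0.8, 0.9 and 0.95. Baseline adjustment removes it.

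**The case against.** The strongest defence is that nothing here is an error. The planned test has its nominal size, meets its own power target after dropout, and matches the endpoint as the protocol words it, namely change in acuity. The adjusted model is already prespecified, so readers will see both estimates. Acuity is one of many secondary outcomes, and no stated decision depends on it. All of that stands, and it limits the point to one of efficiency.

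Three stronger readings are tempting, and the documents do not support them.

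- *A reader might infer that the change score is biased.* Under randomization it is unbiased, and its standard error already covers chance imbalance. What remains is conditional: given the imbalance that actually occurs, the estimate is shifted as shown in the working.
- *A reader might infer that the change score loses precision unless the correlation is 1.* That holds only with equal variances; the general condition is a slope of 1. At ρ = 0.8 with a final SD 1.25 times the baseline SD, the slope is 1 and the gain is zero. Item 4's rule of assigning logMAR 2.0 when no eye can be assessed could widen the final distribution in that direction.
- *A reader might infer a large gain by borrowing the SF-36 correlation of 0.6 or going lower.* That correlation belongs to another instrument, and with a change SD of 6.5 it implies an implausibly narrow spread of acuity.

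The objection that both models will be reported anyway does not settle the matter, because the plan still fixes which of them counts as the test.

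**Conclusion.** The point holds as a modest, free improvement to a secondary outcome. The SAP makes the treatment-only change-score model the principal acuity test and the baseline-adjusted model a supplement, contrary to its own practice for quality of life and macular thickness. In large samples the adjusted model is at least as precise, apart from one degree of freedom.

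Over ρ from 0.6 to 0.95 the gain runs from about 8 power points down to about 1 at 2.63 letters, and from 0.28 down to 0.04 letters in the detectable difference. The upper end of ρ is the more likely, which puts the gain at about 1 to 2 power points. These figures assume equal baseline and final variances, a change SD of 6.5 letters, 97 per arm and one observation per patient. The SAP's own calculation makes the last simplification too, although the model uses up to two eyes. The direction of the result does not depend on these assumptions; its size does.

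**What to change.** Before any unmasked analysis of acuity, amend SAP 3.2.2 item 4 so that the two planned models exchange roles. The principal test becomes the mixed model of final BSCVA on treatment and baseline BSCVA for each eye, with a patient random effect. The treatment-only change-score model stays as a supportive analysis. The 2.63-letter statement in SAP 3.4.2 item 3 can remain, labelled as calculated for the change score and therefore conservative for the adjusted model.

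The cost is a few lines of SAP text. Both models are already specified, and no data, visits or patients are added.

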3.5 Missing data and loss to follow-up

Values of the primary study endpoint (treatment success at six months) cannot be analyzed when the individual is lost to follow-up. We distinguish information which is missing because of possible progression of the underlying condition we wish to treat from information which is lost for some other reason. Earlier, we discussed methods for handling missing values for specific

uveitis fields in individuals. The discussion in this section applies only to loss to follow-up or to dropping out of the study. As emphasized in Carpenter & Kenward (2007), “there can be no universal analysis when data are missing”. Our purpose is to vary the assumptions as well as the methods, to establish that the estimates of the treatment effect are robust as such assumptions are varied.

Our priority is the preservation of the intent to treat principle. We propose to report the results from all of the following methods:

1. The use of regression-based multiple imputation, based on all observed data for the patient.
2. Use of longitudinal generalized linear mixed effects regression, with visit as a covariate, and including a random effect for each person and for each eye within each person, using all the available measurements on each individual
3. Sensitivity analysis in which missing final outcome values are assigned success or failure, and the analysis conducted conditional on these assignments.
4. Analysis of complete cases only (individuals for which the six month follow-up is available)

However, we are proposing that **method 4 (complete case analysis) be considered the primary outcome**, based on recommendation by the DSMB. All other analyses are to be considered supplementary.

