Multiple imputation will be conducted as follows. The following information will be used as regression covariates: (i) age, (ii) gender, (iii) inflammation assessments at all prior time points (anterior cells, vitreous haze, and retinal/choroidal lesions), (iv) steroid dose, (v) anatomic location (by patient, classified as anterior/intermediate or posterior/panuveitis), (vi) anatomic location by history, (vii) maximum steroid dose within the 90 days prior to enrollment, (viii) steroid dose at enrollment prior to randomization or study-related intervention, (ix) country, and (x) site within country. Any additional covariates must be prespecified. A regression model for the missing outcome information will be derived; specifically, a cross-validated procedure to yield the best prediction based on complete subjects will be derived, and ten multiple imputations will be derived from it. The formula in Little and Rubin²⁵ will be used to derive the overall test statistic. All replications will be recorded and reported.

An alternative method (which we propose to use for sensitivity analysis) is hot deck multiple imputation (with ten replications).²⁵ Note that treatment assignment would never be missing. For definiteness, we choose the recursive random partitioning hot deck method used in the R package `rrp` with the default settings (command `rrp.impute`).

The possibility of data-driven modeling may render multiple imputation of an outcome variable undesirable to many reviewers as a primary outcome. An alternative method is to model the treatment success of person i at visit j , Y_{ij} , using generalized linear mixed models, with covariates being site, country, treatment assignment, country-assignment interaction, visit (1:6), and visit-drug interaction (method 2 above). Note that additional statistical modeling will be reported, in which we (a) omit visit-drug interaction, and/or country assignment interaction, (b) add visit-country interaction, or (c) add age or gender as covariates.

We believe carrying forward last observations to be particularly unhelpful in this study, because all patients are on a prescribed steroid taper. We also believe that differential loss to follow-up of well performing patients on one drug or the other could falsely make the poorer drug appear to give more favorable results, so that the complete case analysis must be interpreted with caution.

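### The lead visual acuity analysis fills gaps by carrying the last value forward, and the SAP does not say why its own objection to that method would not apply

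*Combined protocol and SAP*

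**What the plan says.** SAP 3.2.2, Planned Secondary Analyses, item 4, defines the acuity outcome as the change from baseline to the final value. The final value is the month-6 value, or the value at the time of failure for patients who fail. On the model it says: "The primary analysis will use a linear mixed-effects regression, where the outcome variable is the change in BSCVA in each eye". A random effect for patient links the two eyes. On gaps it says: "If at a given visit, vision cannot be assessed, we will carry the last observation forward". An eye that no longer exists at month 6 is given a logMAR of 2.0. Mixed models that control for time and use all of a patient's data are listed only among the additional sensitivity analyses for missing data.

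SAP 3.5 takes a different view of the method: "We believe carrying forward last observations to be particularly unhelpful in this study, because all patients are on a prescribed steroid taper". The same section sets its own scope: "The discussion in this section applies only to loss to follow-up or to dropping out of the study".

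**The concern.** The rule sits in the lead analysis of a named secondary outcome. If an early value stands in for the final one, the comparison partly reflects vision at a higher steroid dose, possibly before the study drug has had its full effect. If a patient fails and acuity is not taken at that visit, a pre-failure value is scored as the final one. In both cases the filled-in value is analysed as if it had been observed, so the uncertainty of the fill-in does not reach the standard error. At stake are the acuity difference between arms and the precision claimed for it. The primary outcome is not affected.

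**Working it through.** **1. The plan's own acuity figure.** SAP 3.4.2 assumes a "standard deviation of the change in visual acuity of 6.5 letters" and states: "The sample size of 108 will provide approximately 80% power to detect 2.63 letters of difference in the change score". SAP 3.4.1 adds: "We assume 10% will be lost to follow-up in the first six months". Evaluable patients per arm are 108 × 0.9 = 97.2. A two-sample t-test with SD 6.5, difference 2.63 and two-sided alpha 0.05 (assumed, since the acuity item does not restate it) has power 0.801. The detectable difference at 80% power is 2.625 letters. With the full 108 per arm, power would be 0.841 and the detectable difference 2.49 letters. The stated figure therefore reproduces, and it already allows for the 10% loss.

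**2. Steroid dose at the visits a value could be carried from.** Protocol Table 6 gives 60 mg for 2 to 4 weeks, then ten one-week steps (50, 40, 35, 30, 25, 20, 17.5, 15, 12.5 and 10 mg), then 7.5 mg. The 7.5 mg level is reached at week 12 to 14. Months are converted as 30.4375 / 7 weeks each, assuming a 60 mg start and no flare.

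| Visit | Week | Planned dose (2-week / 4-week lead-in) | Ratio to the month-6 dose |
|---|---|---|---|
| Month 1 | 4.35 | 35 / 50 mg | 4.7 / 6.7 |
| Month 2 | 8.70 | 17.5 / 25 mg | 2.3 / 3.3 |
| Month 3 | 13.04 | 7.5 / 10 mg | 1.0 / 1.3 |
| Months 4 to 6 | 17.39 and later | 7.5 mg | 1.0 |

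Protocol 3.2.1 puts full drug effect at 6 to 8 weeks. A month-1 value precedes that. A month-4 or month-5 value is past it and at the planned month-6 dose.

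**3. Can a final value be absent?** Yes. In the form schedule (protocol 4.2) the Visual Acuity Form at treatment failure is marked as needed only if applicable. When failure is declared at a non-study visit, every attempt should be made to complete everything. The stated minimum, however, is a clinical eye exam (4.6.1) and a form list without the acuity form (4.6.3). The rule can therefore be called on for patients who fail. With planned success of 40% and 60% (SAP 3.4.1), the number of failures may differ by arm.

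**4. Illustration of size.** Let m be the share of final values that are carried and k the share of the true arm difference they hold. Neither is given in the documents; both are assumptions. Expected difference = 2.63 × (1 − m(1 − k)).

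- m = 0.05, k = 0: 2.63 × 0.95 = 2.50 letters; power at 97.2 per arm 0.76
- m = 0.10, k = 0: 2.63 × 0.90 = 2.37 letters; power 0.71
- m = 0.10, k = 0.5: 2.63 × 0.95 = 2.50 letters; power 0.76
- m = 0.10, k = 0.8: 2.63 × 0.98 = 2.58 letters; power 0.79
- m = 0.20, k = 0: 2.63 × 0.80 = 2.10 letters; power 0.61

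A k near 1 is what values from months 4 and 5 would suggest. Here m is a share of the 97.2 evaluable patients. If instead the carried 10% were the patients lost to follow-up, the analysis would hold 108 per arm, and a difference of 2.37 letters would have power 0.76.

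**5. Unequal gaps.** If 5% of values are carried in one arm and 15% in the other, and carried values overstate final vision by 5 to 10 letters, the bias is (0.15 − 0.05) × 5 to 10 = 0.5 to 1.0 letter. Its sign depends on which arm has more gaps. These inputs are also assumptions.

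**The case against.** A reader might infer that the SAP flatly contradicts itself. It does not. SAP 3.5 confines itself to loss to follow-up and dropout and opens with the primary endpoint. That endpoint has the prednisone dose in its definition, so carrying forward the status of a patient still on the taper is wrong by construction. Acuity has no steroid component, and its rule is triggered when vision cannot be assessed at a visit. This stands against a charge of contradiction. It does not supply a reason for carry-forward: the ground given in 3.5 is the taper in all patients, and item 4 does not say whether dropouts come under its rule.

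A reader might also infer that carried values generally come from the high-dose period. Table 6 does not support that beyond about month 3.

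The rule may touch few values. Vision too poor for letters is still graded by count fingers, hand motion or light perception; an absent eye has its own rule; and acuity at failure is the defined final value, so it will often be observed. This stands, and it is why no size can be given.

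Finally, much is already planned: all-visit mixed models, monthly steroid dose as a predictor in further acuity analyses, and repeat analyses on all available time points (SAP 3.3.3). This also stands. It narrows the point to which analysis leads.

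**Conclusion.** The point holds as a minor one. The lead acuity analysis rests on a single imputation that the SAP criticises elsewhere for a study-wide reason, and acuity is not exempted by any stated argument. The weak spots are values carried from about the first three months and failures without acuity at the failure visit.

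It may be tempting to say that the bias runs toward no difference. The documents do not support a direction: the shrinkage in step 4 of the working assumes that carried values hold less of the arm difference, and unequal gaps could push the estimate either way. No rate of unassessable vision is given, so 2.37 to 2.50 letters at 10% carried is an illustration, and the shift is smaller if the values come from months 4 and 5. The effect on the standard error is a matter of principle here and was not computed. The primary endpoint, for which complete cases lead, is untouched.

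**What to change.** In SAP 3.2.2 item 4:

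- Make the mixed-effects model on all observed Phase I acuity visits the lead analysis, with treatment-by-visit terms and random effects for patient and for eye within patient. The planned version mentions only control for time, so the treatment-by-visit terms must be added.
- Keep the stated outcome. One way is to treat the final occasion (month 6, or the failure visit for patients who fail) as its own level of visit and take the arm contrast there.
- State that acuity measured after a switch to Phase II does not enter the Phase I contrast. Without this, a plain month-6 contrast on all visits would mix in data on the other drug or change the outcome.
- Keep carry-forward only as a sensitivity analysis, and say whether it covers dropouts as well as unassessable vision.

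The cost is a few sentences of SAP text, with no new data. The model relies on gaps being missing at random given the observed visits, which is least certain for failures without a failure-visit value, so sensitivity analyses remain useful.
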